12.7. PK Analysis

The mean and median concentrations of ceftaroline in plasma at the end of infusion will be determined. The proportion of children with plasma ceftaroline concentrations $\geq 1 \mu\text{g/mL}$ at 4 hours after infusion will be determined.

The plasma levels of ceftaroline obtained at 4 hours after the end of a 2 hour infusion will be compared to the ceftaroline MIC for the *S. aureus* isolate recovered causing the osteomyelitis. Ideally, the plasma level should exceed the MIC at this time point which would be for at least 75% of a dosing interval. Assuming the patients do well clinically, there will be no adjustment of the dose even if the target concentration is not achieved at the 6 hour time point following the start of ceftaroline infusion. However, if two subjects do not improve as anticipated, the study will be halted and plasma levels compared to the MICs of the causative *S. aureus* isolates. If plasma levels exceed the MIC and yet the subjects are considered treatment failures in that they are not responded as expected, the investigator would conclude that ceftaroline may not be particularly effective in treating *S. aureus* osteomyelitis in children. If the plasma levels at this time point are below the MIC, a dose modification may be considered but the investigator may decide that studying ceftaroline for this indication is no longer necessary.

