In common with most β -lactams, free drug percentage of time above the minimum inhibitory concentration (%T $>$ MIC) is the most appropriate parameter to predict efficacy of ceftaroline. The pharmacokinetic/pharmacodynamic (PK/PD) relationship for ceftaroline was initially evaluated in the murine neutropenic thigh infection model with several organisms including *S. aureus* (Andes and Craig, 2006). The mean free-drug %T $>$ MIC required for stasis was 26% for *S. aureus*, regardless of the resistance phenotype.

The efficacy of ceftaroline against aerobic gram-positive and gram-negative microorganisms has been established in a variety of animal models of infection, including mouse peritonitis, sepsis, thigh infection, and pneumonia; and in rabbit models of endocarditis, pneumonia, osteomyelitis and meningitis. In the mouse pneumonia model, the efficacy of ceftaroline fosamil was compared with that of vancomycin and linezolid (Study TAK-599/00063). The activity of ceftaroline against MRSA was better than that of vancomycin and linezolid in a neutropenic murine pneumonia model in which 20 mg/kg doses of each drug were administered subcutaneously three times daily for

2 days beginning 1 day after intranasal inoculation. Ceftaroline reduced viable bacterial counts in infected lungs by 4 log units compared to the untreated control ($p < 0.01$), while both vancomycin and linezolid failed to reduce the bacterial counts. When the study was performed by administering the first dose only 2 hours after inoculation, all 3 drugs exhibited bactericidal activity, perhaps because the bacteriostatic agents, vancomycin and linezolid, were only effective during the early stage of infection when the bacterial counts were low, while ceftaroline, being bactericidal, was active even later during the infection.

A dose-fractionation study (P903-M-097) was conducted in a neutropenic murine lung infection model using various clinical isolates of *S. aureus* isolates (MSSA and MRSA, with ceftaroline MICs ranging from 0.5 to 4 mg/L) to define the required magnitude of ceftaroline exposure (ie, free drug concentration above the MIC [$fT > MIC$]) that reliably results in efficacy. Additionally, the efficacy of a human simulated regimen of ceftaroline 600 mg every 12 hours (q12h) administered as a 1-hour intravenous (IV) infusion was evaluated.

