The plasma protein binding of ceftaroline in vitro was generally low (mean \pm SD of 20% \pm 6.1%) and concentration independent in human plasma over the clinically relevant concentration range. In vitro oxidative metabolic studies with liver microsomes demonstrated that the metabolism of ceftaroline is not dependent upon cytochrome P450 enzymes (CYP). In vitro studies in human liver microsomes indicated that neither ceftaroline fosamil nor ceftaroline inhibits the major CYP isoenzymes. In addition, studies in human hepatocytes also demonstrated that ceftaroline fosamil, ceftaroline, and ceftaroline M-1 are not inducers of CYP activity. Therefore, ceftaroline is not expected to inhibit or induce the clearance of drugs that are metabolized by these metabolic pathways in a clinically relevant manner.

No differences in the pharmacokinetics of ceftaroline fosamil, ceftaroline, or ceftaroline M-1 were noted between genders in rats and monkeys. In addition, there was no accumulation of ceftaroline fosamil or ceftaroline after repeated once-daily administration, and only moderate accumulation of ceftaroline M-1 was observed in the repeat-dose toxicology studies.

Safety pharmacology studies were performed in various experimental animal models and in vitro testing systems to examine the effects of ceftaroline fosamil on behavioral and physiological effects, respiratory function, and the cardiovascular system.

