Study CEF-PK-02 was a recently completed Phase 1, open-label, multiple-dose study in healthy adult subjects to assess the concentration of ceftaroline in ELF. Subjects were randomized to receive one of the following dosing regimens: Treatment A - 600 mg ceftaroline fosamil q12h for 3 days with a single dose on Day 4; Treatment B - 600 mg ceftaroline fosamil every 8 hours (q8h) for 3 days with a single dose on Day 4. Twenty-five subjects received each dosing regimen. Plasma samples for PK analysis were collected pre dose and over 24 hours after the final dose on Day 4. Subjects underwent bronchoscopy and BAL at a single time point after the last dose in order to collect ELF. Preliminary data indicate that the ratio of AUCs of free ceftaroline in ELF to free ceftaroline in plasma, assuming 20% protein binding in plasma and no protein binding in ELF, was approximately 22%. All subjects had measurable ceftaroline concentrations in ELF at 1, 2, 4, and 6 hours after the start of the ceftaroline fosamil infusion. Eight out of 10 subjects that underwent BAL 8 hours after dosing had measurable ceftaroline concentration in ELF, and none of the 5 subjects that underwent BAL at 12 hours after dosing had measurable ceftaroline in ELF. These data demonstrate that ceftaroline is able to penetrate into ELF and concentrations of ceftaroline in ELF appreciably exceeded the MIC90 for ceftaroline against *S. aureus* (1 mg/L) at 1 and 2 hours after the start of the ceftaroline fosamil infusion in all subjects. Plasma and ELF concentrations were similar for the 2 dosing regimens, with the q8h regimen showing slightly (approximately 15% to 20%) higher concentrations on average. Ceftaroline appeared to be eliminated from plasma and ELF at a similar rate.

Ceftaroline fosamil at a dose of 600 mg (or 400 mg if the subject had renal impairment) q12h was well tolerated in 693 adult subjects in the 2 completed Phase 3 CAP studies. As shown in these studies,

monotherapy with ceftaroline fosamil at a dose of 600 mg administered as a 1-hour IV infusion q12h for 5 to 7 days is effective for the treatment of CABP caused by susceptible isolates of the following gram- positive and gram-negative microorganisms: *S. pneumoniae* (including cases with concurrent bacteremia), MSSA, *H. influenzae*, *K. pneumoniae*, *K. oxytoca*, and *E. coli*.

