4.4. Rationale for Ceftaroline Fosamil Dosage Regimen

The selected ceftaroline dose regimens (15 mg/kg [600 mg if > 40 kg] as a 2-hour infusion q8h) are expected to achieve PK/PD targets associated with 1-log kill of *S. aureus* in the murine pneumonia model for organisms with MIC values up to 1 mg/L in > 90% of patients 2 months to < 18 years. The median Cmax value in children 1 year to < 18 years with normal renal function dosed with 15 mg/kg q8h as a 2-hour infusion predicted to be less than the median Cmax value in adults dosed with 600 mg q8h as a 1-hour infusion. The median AUC0-24h in children 1 year to < 18 years dosed with the above regimen is predicted to be up to 15% greater than in adults dosed with 600 mg q8h. The median f T > MIC for an MIC of 1 mg/L is predicted to be 84-93% for the recommended pediatric dose regimens compared to 100% in adults dosed with 600 mg q8h.

Initially, the sponsor believed that a dose of 15 mg/kg q8h to match the dose of 600 mg q8h in adults was appropriate for children from 6 months to <18 years. However, based on findings in the pediatric ABSSI and CABP studies, a lower dose of 10 mg/kg q8h is more appropriate for children from 6 months to < 2 years in order to avoid higher AUC values. The 10 mg/kg q8h dose in this age range is expected to result in a median fT (unbound drug time over MIC) > MIC of 78-88% for an MIC of 1 mg/L and 58-66% for an MIC of 2 mg/L. This would give nearly 100% target attainment for a target of 50% at an MIC of 1 mg/L. The higher dose of 15 mg/kg q8h would still be appropriate for children 2 and older.

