5.2. Secondary Objectives

- Evaluate efficacy of ceftaroline in pediatric subjects with acute hematogenous osteomyelitis at the end of IV therapy, at the end of total therapy (anticipated to be at 4 to 6 weeks after enrollment), and at one year after enrollment.
- Evaluate clearance of *S. aureus* bacteremia if blood cultures initially positive.
- Assess proportion of patients with plasma levels of ceftaroline that exceed 1 µg/mL for over 60% of a dosing interval.

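### Section 12.7 sets plasma ceftaroline against the isolate MIC without a protein-binding correction; if the assay is total drug, levels of 1.00 to 1.25 × MIC are classed as above the MIC when free drug is not

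*Combined protocol and SAP*

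**What the plan says.** **The comparison.** Section 12.7: "The plasma levels of ceftaroline obtained at 4 hours after the end of a 2 hour infusion will be compared to the ceftaroline MIC" of the causative isolate. It then states what this time point stands for: "Ideally, the plasma level should exceed the MIC at this time point which would be for at least 75% of a dosing interval". The same section reports the proportion of children at or above 1 µg/mL at 4 h.

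**What depends on it.** If two subjects do not improve, the study is halted and levels are compared with the MICs. One branch begins "If plasma levels exceed the MIC and yet the subjects are considered treatment failures" and ends in a conclusion that the drug may not work well for this indication. In the other branch, with levels below the MIC, a dose change may be considered or the indication may be dropped.

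**The trial's PK objective.** Section 5.2: "Assess proportion of patients with plasma levels of ceftaroline that exceed 1" µg/mL, for more than 60% of a dosing interval. Section 12.3 repeats this as an endpoint. Neither mentions free drug.

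**The pharmacological basis.** Section 4.2.2 names "free drug percentage of time above the minimum inhibitory concentration" as the best predictor of efficacy. It gives 41.4% as the free-drug exposure for a 1-log reduction in the mouse lung model. It also states: "The plasma protein binding of ceftaroline in vitro was generally low", with mean 20%, SD 6.1%, independent of concentration. The adult lung-fluid study in section 4.2.4 was analysed "assuming 20% protein binding in plasma". Section 4.4 justifies the regimens by unbound time over the MIC, with predicted medians of 84–93% at 15 mg/kg and 78–88% at 10 mg/kg for an MIC of 1 mg/L. Of the 10 mg/kg dose it says: "This would give nearly 100% target attainment for a target of 50% at an MIC of 1 mg/L".

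**The assay.** Sections 6.1 and 9.8.3 ask for concentrations in plasma and do not say total or unbound.

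**The concern.** The doses are justified on one scale and the trial's readout is defined on another, or at least on a scale that is not stated. MICs are compared with free drug throughout sections 4.2.2 and 4.4. Section 12.7 compares them with an unqualified plasma level.

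At stake is how a small number of poor responses is read. Two children are enough to trigger the comparison, and its two branches carry different messages about the drug. Section 4.2.2 puts the MIC90 for *S. aureus* at typically 1 mg/L, the same value as the fixed threshold, so levels close to the MIC are plausible. The optional interim PK analysis in section 12.6, which may be used to confirm or adjust the dose, is equally silent on free or total.

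**Working it through.** **Inputs**
- Infusion 2 h, sample 4 h ± 30 min after its end, dosing every 8 h (sections 8.1, 9.8.3).
- Binding 20%, SD 6.1% (section 4.2.2).
- Terminal half-life 2.0–2.6 h (section 4.2.4). This is an adult value; no paediatric value is given, so using it is an assumption.
- Time is counted from the start of infusion, as the plan's 75% implies.

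**1. The plan's own figure.** (2 + 4)/8 = 75.0%, which matches 12.7. The ± 30 min window gives 5.5/8 = 68.75% to 6.5/8 = 81.25%.

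**2. Total level at which free drug equals the MIC.** Total = MIC/(1 − binding).
- 20%: 1/0.80 = 1.25 × MIC.
- 13.9% (−1 SD): 1/0.861 = 1.16 × MIC.
- 26.1% (+1 SD): 1/0.739 = 1.35 × MIC.

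At mean binding, the children who change class at the 4 h point are those with a total level of 1.00–1.25 × MIC.

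**3. The same shift in time.** With first-order decline, shift = half-life × log2(1.25) = half-life × 0.322.
- 2.0 h: 0.64 h, or 8.0% of 8 h.
- 2.6 h: 0.84 h, or 10.5% of 8 h.

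A child whose total level equals the MIC at 6 h therefore has free drug above the MIC for 75 − 8.0 = 67.0% to 75 − 10.5 = 64.5% of the interval.

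**4. Does this overstate attainment of the 60% objective?** 60% of 8 h is 4.8 h, which is 1.2 h before the sample. The total level at 6 h that corresponds to exactly 60% free time above 1 mg/L is [1/(1 − binding)] × 2^(−1.2/half-life).

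| Binding | Half-life 2.0 h | Half-life 2.6 h |
|---|---|---|
| 20% | 0.82 µg/mL | 0.91 µg/mL |
| 26.1% | 0.89 µg/mL | 0.98 µg/mL |

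All are below 1 µg/mL, so a total level of 1 µg/mL at 6 h generally implies more than 60% on the free scale. Exceptions arise at the edges. A sample at 3.5 h with half-life 2.6 h gives 68.75 − 10.5 = 58.3% (unrounded shift). At that early sample, 26.1% binding gives 57.8% (2.0 h) and 54.6% (2.6 h). Binding of 32.2% (+2 SD) with half-life 2.6 h and a sample on time gives 56.8%. All of these still exceed 50% and 41.4%.

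**5. Illustration of how many children change class at 4 h.** Assumptions: log-normal levels with CV 30–50% (not in the documents), the adult half-life, 20% binding, and median free level at 6 h = 2^((8f − 6)/half-life), where f is the median predicted in section 4.4.

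| Median f | P(total > 1) | P(free > 1) | Gap, points | Of 18 children |
|---|---|---|---|---|
| 84% | 81–95% | 66–80% | 14–18 | 2.5–3.2 |
| 93% | 90–99% | 79–96% | 4–11 | 0.7–2.0 |

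If the median is 78%, the low end for the 10 mg/kg regimen, the gap reaches 25 points. Across the rows shown, the probability of at least 60% free time above 1 mg/L is 86–99.9%, and in each scenario it is at or above P(total > 1). This agrees with step 4.

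**The case against.** The strongest reply is that little harm follows. The trial's stated target is a plasma level for 60% of the interval, and the sample is taken at 75%. The 15-point margin generally absorbs the 8 to 10.5 points lost to binding. This stands. A reader might infer that target attainment in this trial is overstated; step 4 shows that, against the 60%, 50% and 41.4% figures, in general it is not.

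A reader might also infer that a failing child in the 1.00–1.25 × MIC band was under-exposed and is wrongly read as a failure of the drug. The documents do not support that either. At mean binding and on-time sampling, such a child still has about 64.5% or more free time above the MIC, beyond both free-drug figures in the protocol. What is missed is the 75% point, which 12.7 itself presents as an ideal, and the consequences in 12.7 are worded as discretionary.

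Three further points stand. That the assay measures total drug is an inference. The 84–93% and 78–88% in section 4.4 are median shares of an interval, while the endpoint is a share of children, and one sample per child cannot estimate the former. And the ± 30 min window alone moves the level by about 14–19% (2^(0.5/2.6) = 1.14; 2^(0.5/2.0) = 1.19), not far short of the 25% at issue.

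None of this answers the remaining defect: 12.7 classifies a level as above or below the MIC without saying which level, and the protocol's own pharmacology says free drug is the one that counts.

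**Conclusion.** The point holds in a limited form. Section 12.7 does not define its comparison on the scale that the protocol says predicts efficacy. If the assay is total drug, levels of 1.00–1.25 × MIC (upper limit 1.16–1.35 for binding ± 1 SD) are placed above the MIC when free drug is at or below it. The plan's 75% then corresponds to about 64.5–67% free. In the illustration with medians of 84–93%, roughly one to three of 18 children change class at the 4 h point.

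These sizes rest on 20% binding measured in vitro, an adult half-life, first-order decline and, for the count of children, an assumed CV. The result affects the above/below-MIC classification and the 4 h proportion in 12.7. It does not show general overstatement of the 60% objective.

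**What to change.** 1. In sections 6.1, 9.8.3 and 12.7, state whether the assay measures total or unbound ceftaroline.
2. If total, make the above/below-MIC comparison in 12.7 on 0.8 × the measured level, with a sensitivity range for binding of 14% to 26% (factors 0.86 to 0.74). If the sponsor prefers total levels, give the reason.
3. Report the proportion of children with free drug above 1 µg/mL at 4 h beside the total-concentration proportion.
4. Do not carry a cut-off of total > 1.25 µg/mL into the 60% endpoint in 5.2 and 12.3. At 6 h it tests about 75% free time, which is stricter than the objective and would understate its attainment.
5. Reconcile the 60% objective, the 75% time point in 12.7 (4 h after infusion) and section 12.1, which gives 5–6 h after infusion, or 87.5–100% of the interval.

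What follows for dosing or stopping from either branch of 12.7 is left to the sponsor.

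Cost: wording changes and one multiplication per sample, with no new samples or assays. The reported proportion above the MIC may be slightly lower.

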4.2.2. Summary of Microbiological and Pharmacology Studies

Ceftaroline displays broad antibacterial activity against aerobic and anaerobic gram-positive and gram-negative bacteria. Like other β -lactams, ceftaroline is bactericidal and targets PBPs to inhibit bacterial cell wall biosynthesis. Ceftaroline binds with high affinity to PBPs from MSSA with additional ability to bind efficiently to PBP2a, the PBP present in MRSA responsible for methicillin resistance. Ceftaroline also retains activity against contemporary resistant organisms including both hospital-acquired methicillin- resistant *S. aureus* (HA-MRSA) and CA-MRSA, including *S. aureus* isolates resistant to clindamycin, in addition to vancomycin-intermediate *S. aureus* (VISA) and vancomycin-resistant *S. aureus*.

The minimum concentration required to inhibit the growth of 90% of organisms (MIC90) for *S. aureus* isolates is typically 1 mg/L (Study NSR-P903-M-071). Ceftaroline also has potent activity against isolates of streptococci, including *Streptococcus viridans* species, with MIC90 values typically < 0.12 mg/L. Erythromycin resistance in the streptococci has not been associated with increased MICs to ceftaroline. Against the Enterobacteriaceae, MIC90 values for ceftazidime-susceptible isolates (ie, presumed non-extended-spectrum β -lactamase-producing, non-AmpC β -lactamase-overexpressing) are typically ≤ 1 mg/L, as seen with *Citrobacter freundii*, *Enterobacter cloacae*, *E. coli*, *K. pneumoniae*, *K. oxytoca*, and *Proteus mirabilis* isolates. Ceftazidime-resistant strains had elevated MIC values to ceftaroline. Ceftaroline is less active against the indole-positive Proteae, including *Morganella morganii* and *Providencia* spp. (MIC90 > 32 mg/mL). Ceftaroline has little in vitro activity against *Pseudomonas aeruginosa*.

Resistance to ceftaroline develops at low frequency in vitro. For *S. aureus*, spontaneous resistant mutants to 4 times MIC of ceftaroline have not been observed ($\leq 10-10$). In various animal models of infection caused by either gram-positive or -negative bacteria, including MRSA and VISA, ceftaroline was shown to be highly effective.

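### Section 12.7 draws an efficacy conclusion from two failing children with levels above the MIC, without using the number treated or the successes; at the protocol's own rates that is weak evidence

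*Combined protocol and SAP*

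**What the plan says.** Section 12.7 (PK Analysis) sets a trigger: "if two subjects do not improve as anticipated, the study will be halted and plasma levels compared to the MICs" of the causative isolates. It then splits on the level. The first branch reads "If plasma levels exceed the MIC and yet the subjects are considered treatment failures in that they are not responded as expected", and its consequence is "the investigator would conclude that ceftaroline may not be particularly effective in treating *S. aureus* osteomyelitis in children". In the second branch, levels below the MIC, a dose modification may be considered, or the investigator may decide that the indication need not be studied further.

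The level is the sample taken 4 hours after the end of a 2-hour infusion: "Ideally, the plasma level should exceed the MIC at this time point which would be for at least 75% of a dosing interval".

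Other sections that bear on this:
- Section 6.2 sizes the trial at 18 by A'Hern's single-stage design, for rates of 0.50 against 0.80 with type 1 error 0.05 and power 80%. It gives no cut-off and does not name the endpoint.
- Section 7.10 also stops the study at two treatment failures, with no denominator.
- Section 12.5 lists clinical response by subject and pathogen, and clinical outcome at the end of therapy and at one year.
- Section 4.4 gives the predicted exposure: "The median f T > MIC for an MIC of 1 mg/L is predicted to be 84-93% for the recommended pediatric dose regimens". For the 10 mg/kg regimen it gives a median free time above "MIC of 78-88% for an MIC of 1 mg/L and 58-66% for an MIC of 2 mg/L".
- Section 4.2.2 states that the MIC90 "for *S. aureus* isolates is typically 1 mg/L".

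**The concern.** The inputs to the conclusion are two children chosen because they failed, and their two level/MIC comparisons. Nothing in section 12.5, or elsewhere in 12.7, is tied to that sentence. A statement about whether adequate exposure cures has to compare failures with everyone who had adequate exposure, and here the successes are left out. The wording commits the investigator in advance to one reading of a pattern that an effective drug can also produce. In a single-arm trial of 18 children, an early interpretation of this kind may shape whether the indication is studied further. The point concerns the inference only. Whether the study should halt at two failures is a separate matter.

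**Working it through.** **1. Reproduce the design (section 6.2).** Find the smallest n with a cut-off r such that P(X ≥ r | n, 0.50) ≤ 0.05 and P(X ≥ r | n, 0.80) ≥ 0.80, exact binomial.

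| n | r | type 1 error | power |
|---|---|---|---|
| 16 | 12 | 0.038 | 0.798 |
| 17 | 13 | 0.025 | 0.758 |
| 18 | 13 | 0.048 | 0.867 |

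No smaller n qualifies, so the stated 18 is reproduced. The implied cut-off is 13 successes of 18. If the rate is clinical success, up to 18 − 13 = 5 failures are compatible with rejecting 0.50.

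**2. How often two failures occur.** With independent failures at rate q, P(at least 2 in 18) = 1 − (1−q)^18 − 18q(1−q)^17.

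| true success | q | calculation | P(at least 2 failures) |
|---|---|---|---|
| 50% | 0.50 | 1 − 0.000004 − 0.000069 | 0.9999 |
| 80% | 0.20 | 1 − 0.0180 − 0.0811 | 0.901 |
| 90% | 0.10 | 1 − 0.1501 − 0.3002 | 0.550 |
| 95% | 0.05 | 1 − 0.3972 − 0.3763 | 0.226 |

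Between the two rates that the protocol names, the ratio is 0.9999/0.901 = 1.11. Reaching two failures at some point hardly distinguishes them.

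**3. What the missing denominator carries.** The chance that the second failure is the n-th child is (n−1)q²(1−q)^(n−2). The ratio of this at 50% success to that at 80% success is (0.25/0.04) × (0.5/0.8)^(n−2) = 6.25 × 0.625^(n−2).
- n = 3: 6.25 × 0.625 = 3.9, favouring 50% success.
- n = 5: 6.25 × 0.244 = 1.5.
- n = 6: 6.25 × 0.153 = 0.95, now slightly favouring 80% success.
- n = 18: 0.0034, strongly favouring 80% success.

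So the same two failures point in opposite directions according to when the second one occurs, and the sentence in 12.7 does not use this. The calculation assumes that outcomes become known in order of treatment.

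**4. The level check.** The sample is at 2 + 4 = 6 hours of an 8-hour interval, which is 75%. The predicted median free times above an MIC of 1 mg/L are 84–93% and 78–88% (section 4.4). Both ranges lie above 75%, so more than half of children are expected to pass at that MIC, which is also the stated MIC90. The documents give no spread around these medians. With a lognormal level, the adult half-life of 2.0–2.6 h (section 4.2.4), 20% protein binding (section 4.2.2) and an assumed CV of 30–50%, about 73–99% would pass on total plasma level. At an MIC of 2 mg/L the 10 mg/kg medians (58–66%) fall below 75%, and about half or fewer would pass.

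**5. What the check adds.** If passing is unrelated to outcome, it multiplies both probabilities in step 2 by the same factor and the ratio stays 1.11. Suppose instead that under an effective drug (80% success) 10% of children have low levels and only 50% of those succeed; both figures are assumptions. Success in the other 90% is then (0.80 − 0.10 × 0.50)/0.90 = 0.833, and the chance that a failing child passes is 0.90 × 0.167/0.20 = 0.75. Under an ineffective drug, with outcome unrelated to level, it is 0.90. For two failing children the check contributes 0.90²/0.75² = 1.44, and the whole rule 1.44 × 1.11 = 1.6. That is some evidence, but weak.

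**The case against.** The strongest reply is that the level check is not offered as a test of efficacy. It sorts failures into those explained by low exposure and those that are not, and a high pass rate is what the dose was chosen to achieve. That stands: the check validly rules out one explanation of a failure. It does not turn two selected failures into evidence about the drug.

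A second reply is that the wording is hedged, the primary objective is safety, and section 12.5 still reports response for all children. The hedge is real, and nothing says that the 12.7 sentence replaces the 12.5 results. Even so, the sentence prescribes a conclusion, and the 12.5 results do not feed it.

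A third is that the probabilities in step 2 are those of reaching the halt. They are, but the conclusion cannot be drawn without that trigger, so they also bound how often it is drawn.

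Three stronger readings are tempting and should not be taken:
- **The rule cannot separate an effective from an ineffective drug.** It can to some degree. Two failures occur in 23% of trials at 95% success, against over 99.9% at 50%. The level check adds nothing only if level and outcome are unrelated, and section 4.2.2 treats time above the MIC as the best predictor of efficacy.
- **A firm rate at which the full rule would wrongly fire.** This needs the share of children passing the check, which the documents do not give. It also needs both failing children to have an *S. aureus* isolate and a PK sample. Entry is on suspected disease, and the sample is only to be attempted.
- **Two failures in 18 as the typical case, an 89% success rate condemned.** With a halt at the second failure, that result needs the 18th child to be the second failure. Its probability is 17q²(1−q)^16, or 3.2% at q = 0.10 and 1.9% at q = 0.20. An ordinary exact interval would also treat n as fixed.

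**Conclusion.** The concern holds in this form. Section 12.7 lets two failing children with levels above the MIC support a statement of doubtful efficacy, with no denominator, no successes and no level/MIC in the successes. At the protocol's own rates this is weak evidence: the trigger is met in over 99.9% of trials at 50% success and in 90% at 80% success. It becomes more informative only if an effective drug succeeds more often, with 55% at 90% success and 23% at 95%. The level check helps to exclude under-exposure and adds little on efficacy.

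These figures assume independent failures and up to 18 children. The comparison with the 13-of-18 cut-off further assumes that the section 6.2 rate is clinical success. The statement that more than half of children pass rests on predicted medians at an MIC of 1 mg/L and does not extend to 2 mg/L.

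**What to change.** In section 12.7, replace the sentence that draws the efficacy conclusion with text to this effect:
- Any statement on effectiveness rests on all treated children. Report failures over the number treated at that point, with an exact interval, and note that the number treated is random if the study halts at the second failure.
- For all children with an *S. aureus* isolate and a PK sample, tabulate level/MIC by success and failure.
- In failing children, use the level check only to assess under-exposure.

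The halt itself appears in both 7.10 and 12.7. Those passages need to be reconciled by the investigator and the Data Review Committee, and this point takes no position on it.

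The cost is a change of wording and one small table from data already planned, with no new samples or patients. The downside is that no efficacy verdict is issued if the study halts early.
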